3.7 Center pooling strategy

Each study site will contribute to the summaries of data from Part A1 according to the number of evaluable participants recruited; no separate summaries for each site will be presented.

3.8 Coding dictionaries

Adverse events (AEs) and medical history will be coded by UCB, using the latest available version of the Medical Dictionary for Regulatory Activities (MedDRA®) (Version 25.1 or higher). The National Cancer Institute Common Terminology Criteria for AEs (Version 5.0) (NCI CTCAE) dictionary will also be used by the investigator to assign CTCAE severity grades to each adverse event (AE) and will be merged with the clinical database to define a CTCAE code and term to be used in the summaries of TEAEs by maximum CTCAE severity grade.

Medications (including prior anti-cancer systemic therapies) will be coded according to the World Health Organization Drug Dictionary (WHODD) (Version SEP/2020). Medical procedures will not be coded.

The versions of the coding dictionaries used will be displayed in the relevant TFLs.

3.9 Changes to protocol-defined analyses

The following changes to the protocol have been incorporated into the SAP:

- Other safety data have not been defined as safety endpoints in the protocol, e.g. clinical laboratory data, vital signs, ECG, echocardiogram, ECOG performance status and physical examination. These have been listed in [Section 2.2.1](#) of the SAP as ‘other safety endpoints’ to support the characterization of the safety profile of UCB6114 and to provide supporting evidence of any measurements that are deemed abnormal and clinically significant and reported as an AE.
- ECOG performance status is defined as an efficacy assessment in Section 9.6.2 of the protocol, however, it will also be assessed from a safety perspective in Part A1. The SAP therefore includes ECOG performance status as both a safety endpoint ([Section 2.2.1](#)) and an exploratory efficacy endpoint (changes from Baseline during Part A1 in [Section 2.2.3](#)).

4 STATISTICAL/ANALYTICAL ISSUES

4.1 Adjustments for covariates

Not applicable.

4.2 Handling of dropouts or missing data

There will be no imputation of missing data unless otherwise stated in the sections below.

4.3 Pharmacokinetics and pharmacodynamics

The reporting and handling of missing values and values that are BLQ in the TFLs is described in [Section 3.1](#). Zero values will be assumed at the predose timepoint on Day 1 of Cycle 1.

4.4 Safety laboratory data

The rules for handling values that are BLQ in the safety laboratory data will be the same as those described for PK data in [Section 3.1](#). Any values above the limit of quantification (ALQ) will be assigned as the value of upper limit of quantification.

4.4.1 Dates and times

Partial dates may be imputed for the following reasons:

- Classification of AEs as treatment-emergent;
- Classification of medications recorded on the concomitant medications log as prior or concomitant;
- Calculation of time since initial diagnosis, time since completion of most recent line of prior anti-cancer systemic therapy and time since progression/relapse on most recent line of prior anti-cancer systemic therapy.

Imputed dates will not be shown in the listings; all dates will be displayed as reported in the database.

The following rules will be applied for partial onset/start dates:

- If only the month and year are specified and the month and year of the first dose of UCB6114 is not the same as the month and year of the start date then the 1st of the month will be used, or the date of the Screening visit if this is later (if the latter imputation results in an end date that is earlier than the start date, then the 1st of the month will be used);
- If only the month and year are specified and the month and year of the first dose of UCB6114 is the same as the month and year of the start date, then the date of the first dose of UCB6114 will be used. If this results in an imputed start date that is after the specified end date, then the 1st of the month will be used, or the date of the Screening visit if this is later (if the latter imputation results in an end date that is earlier than the start date, then the 1st of the month will be used). If the imputed date is the same date as the date of the first dose of UCB6114 then, for AEs, the event will be regarded as treatment-emergent. For medications, the medication will be classified as concomitant;
- If only the year is specified, and the year of the first dose of UCB6114 is not the same as the year of the start date then January 01 will be used;
- If only the year is specified, and the year of the first dose of UCB6114 is the same as the year of the start date, then the date of the first dose of UCB6114 will be used. If this results in an imputed start date that is after the specified end date, then January 01, or the date of the Screening visit if this is later will be used (if the latter imputation results in an end date that is earlier than the start date, then January 01 will be used). If the imputed date is the date of the first dose of UCB6114 then, for AEs, the event will be regarded as treatment-emergent. For medications, the medication will be classified as concomitant.
- If the onset/start date is completely missing then the onset/start date will be imputed to the date of first dose of UCB6114 and therefore, for AEs, the event will be regarded as

treatment-emergent and, for medications, the medication will be classified as concomitant.

The following rules will be applied to partial end/stop dates:

- If only the month and year are specified, then the last day of the month will be used;
- If only the year is specified, then December 31 of the known year will be used;
- If the stop date is completely unknown, the stop date will not be imputed.

Note that the start date or stop date of a prior medication (partial or otherwise) should not be imputed past the Screening visit date - 1.

In addition to onset and stop dates, the onset and end times of AEs occurring on the day of UCB6114 infusion will be collected on the eCRF. Onset and end times may also be recorded for other AEs that do not occur on the same day as the UCB6114 infusion. The duration of AEs with onset and end times will be calculated in days and hours:minutes (hh:mm) as:

$$\text{Duration of AE} = \text{End Date and Time} - \text{Onset Date and Time}$$

In cases where only the onset and stop dates are recorded for an AE, the duration of an AE will be calculated in days as:

$$\text{Duration of AE} = (\text{Stop Date} - \text{Onset Date}) + 1$$

Note that for participants who have an AE which starts and stops on the same day, but with only a start time or only a stop time recorded, it will be assumed that their AE started from 00:00 (if no start time is recorded) and ended at 23:59 (if no stop time is recorded) on that day.

If the date of a participant's initial diagnosis is incomplete, it will be imputed to the most recent feasible date for the calculation of time since initial diagnosis as follows:

- If only the day is missing, it will be imputed to the last day of the known month;
- If the day and month are missing, it will be imputed to December 31 in the known year;
- If the date of initial diagnosis is completely missing, then time since initial diagnosis will not be calculated.

The above date imputation rules will be applied to partially missing stop dates of a participant's last prior anti-cancer systemic therapy as well as partially and completely missing dates of progression/relapse on last prior anti-cancer systemic therapy.

In cases where the stop date of a participant's last prior anti-cancer systemic therapy and/or a participant's date of progression on last line of prior anti-cancer systemic therapy is completely missing, the participant's Screening date -1 will be used in the calculation of the time since completion of most recent line of prior anti-cancer systemic therapy and the time since progression/relapse on most recent line of prior anti-cancer systemic therapy, respectively.

Note that partial dates will not be imputed as a participant's first dose of UCB6114 in the calculation of time since initial diagnosis, time since completion of most recent line of prior anti-

cancer systemic therapy and time since progression/relapse on most recent line of prior anti-cancer systemic therapy.

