In the overview summary of TEAEs, participants will be counted as having at least one TEAE with CTCAE severity grade ≥ 3 , and in the summary of TEAEs by maximum CTCAE severity grade, participants will be counted as having at least one TEAE in the following categories: ‘Grade 1’, ‘Grade 2’, ‘Grade 3’, ‘Grade 4’, ‘Grade 3 or 4’, ‘Grade 5’, and ‘Grade ≥ 3 ’. Events for which no CTCAE severity grade is recorded by the investigator but an intensity is recorded instead, the intensity of this event will be assigned to a CTCAE severity grade for the purpose of these summaries, i.e. ‘Mild’ will be included as ‘Grade 1’, ‘Moderate’ will be included as ‘Grade 2’, ‘Severe’ will be included as ‘Grade 3’ and ‘Life Threatening’ will be included as ‘Grade 4’ and, if the participant dies due to the event, it will be included as ‘Grade 5’. The determination of whether the event is life threatening or results in death will be based on the reason for seriousness recorded as life-threatening or death on the eCRF, or on the event having a fatal outcome. Otherwise, if both the CTCAE severity grade and intensity is missing then the CTCAE severity grade in these summaries will be missing. A study participant who experiences the same event multiple times will be included in the highest severity grade category in the summary of TEAEs by maximum CTCAE severity grade.

A glossary of all AEs will be presented including the MedDRA® SOC, HLT, PT, reported term and LLT.

A listing of all AEs will be presented by study participant for the ES. The listing will include the onset date and stop date of the event (including relative days) and also the onset times and stop times of events where available. The period of onset of AEs will also be presented on this listing.

Period of onset of AEs will be defined as follows for the purpose of the listing:

- If the AE has an onset date prior to the date of the Screening visit, then Period=Pre-study;

- If the AE has an onset date on or after the date of the Screening visit and has an onset date and time prior to the start time of UCB6114 infusion on Day 1 of Cycle 1 then Period=Screening;
- If the AE has an onset date and time on or after the start time of UCB6114 infusion on Day 1 of Cycle 1 and up to the date and time of the start of Cycle 2 (i.e. prior to the start time of the UCB6114 infusion on Day 1 of Cycle 2) then Period=Cycle 1;

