8.2.2 Infusion-related reactions

Infusion-related reactions are defined as hypersensitivity reactions, anaphylactic reactions and cytokine release syndrome with onset within 24 hours after the start of the UCB6114 infusion.

All potential infusion-related reactions will be identified programmatically and will then undergo medical review for confirmation based on participant characteristics and other signs and symptoms. The final assessment from the medical review will be used in the programming to ensure that all infusion-related reactions are flagged correctly in the listings and included in the relevant summaries.

Hypersensitivity reactions will be programmatically identified as any TEAE with a PT from both a narrow and broad scope search of category A terms of the ‘Hypersensitivity’ SMQ.

Anaphylactic reactions will be programmatically identified using an algorithmic approach based on the ‘Anaphylactic Reaction’ SMQ. Further details on this algorithm are given in [Section 13.1](#). Note that if the MedDRA® version is increased from 25.1 during the study, any changes to the terms included in the ‘Anaphylactic Reaction’ SMQ should be applied.

Cytokine release syndrome will be programmatically identified as any TEAE with a PT of ‘Cytokine release syndrome’ from the broad scope search of category A terms of the ‘Hypersensitivity’ SMQ. Since this disorder is characterized by fever, headache, tachycardia, hypotension, rash, tachypnoea and/or hypoxia, a further medical review of participants with these events occurring within 24 hours after the start of the infusion of UCB6114 will be performed to confirm any further infusion-related reactions.

Note that any other AEs (i.e. not identified as infusion-related reactions using the rules above) which result in a temporary interruption or permanent discontinuation of a UCB6114 infusion will not be considered as an infusion-related reaction.

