If a participant has a TEAE which codes to a PT included in Category A, then the event will be flagged as an anaphylactic reaction. Note that participants with a TEAE coded to a PT='Type 1 hypersensitivity' will also be flagged as having a hypersensitivity reaction as this PT is also included in the Category A narrow search for the 'Hypersensitivity' SMQ.

OR

If a participant has a TEAE which codes to a PT included in Category B **AND** has a TEAE which codes to a PT included in Category C, **and both TEAEs have the same start date**, then both events will be flagged as anaphylactic reactions.

OR

If a participant has a TEAE which codes to a PT included in Category D **AND** has (either a TEAE which codes to a PT included in Category B **OR** a TEAE which codes to a PT included in Category C), **and both TEAEs have the same start date**, then both events will be flagged as anaphylactic reactions.

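### Two timing rules in both SAPs, same-date pairing for anaphylaxis and an unrestricted 00:00 start time, do not fit the 24-hour definition of an infusion-related reaction

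*SAP*

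**What the plan says.** The relevant rules are the same in substance in the two SAPs.

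- **Definition (8.2.2 in both).** Hypersensitivity reactions, anaphylactic reactions and cytokine release syndrome count as infusion-related reactions if they occur "with onset within 24 hours after the start of the UCB6114 infusion". Candidates are found by program and then confirmed by medical review. A further review looks at participants with a short list of cytokine-release symptoms (fever, headache, tachycardia, hypotension, rash, tachypnoea, hypoxia) within 24 hours.
- **Anaphylaxis algorithm (13.1 in both).** One Category A term is enough. Otherwise a B+C, D+B or D+C pair is needed, "and both TEAEs have the same start date".
- **Missing clock times (Part A 4.2.3, Part A1 4.4.1).** For an event "which starts and stops on the same day, but with only a start time or only a stop time recorded", the SAP states that "it will be assumed that their AE started from 00:00 (if no start time is recorded"; a missing stop time becomes 23:59. The note follows the formulas for AE duration.
- **Collection of times (same sections).** Times are collected for events on the infusion day. For other days, Part A1 says: "Onset and end times may also be recorded for other AEs that do not occur on the same day as the UCB6114 infusion".
- **Period of onset (8.2 in both).** In Part A1, an event on or after the Screening visit that "has an onset date and time prior to the start time of UCB6114 infusion on Day 1 of Cycle 1 then Period=Screening". TEAE status, by contrast, is set by start date.

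**The concern.** A 24-hour window that opens with a daytime infusion always runs past midnight, so rules tied to the calendar date cannot reproduce it. The pairing rule is explicit and will be programmed as written. The 00:00 rule is worded as a general assumption about when the event began, and a programmer could carry it into relative time, the 24-hour test and the period of onset.

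Infusion-related reactions have their own summary table in 8.2. Monitoring them is one of the two stated reasons for sentinel participants, and Part A1 explores shorter infusions. Its cohorts enrol up to 8 participants, so one participant classified differently moves a cohort's incidence by 1/8 = 12.5 percentage points. That arithmetic holds for any single event; it does not show how often misclassification would occur.

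**Working it through.** The SAPs give no figure on this point to reproduce, so the check applies their rules to dated and timed events.

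**Inputs.** Window: 0 to 24 hours (1,440 minutes) from infusion start (8.2.2). Relative time: onset time minus infusion start time (3.2.1). Pairing: equal calendar start dates (13.1). Missing start time: 00:00 (Part A 4.2.3, Part A1 4.4.1). Assumption: the infusion starts at clock hour h, between 08:00 and 16:00. The SAPs give no infusion start times.

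**1. Pairing.** Take an infusion at 10:00, wheezing (Category B) at 23:30 and angioedema (Category C) at 00:30 the next day.

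- 23:30 − 10:00 = 810 minutes, inside the window.
- 00:30 next day − 10:00 = 870 minutes, inside the window.
- The onsets are 60 minutes apart but on different dates, so 13.1 does not flag the pair.

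The other routes to identification are limited. Neither term is in Category A. The main review confirms cases the program has found. Neither term is on the cytokine-release symptom list. The hypersensitivity search may catch one of them, but the SAPs do not print its terms; a hit there would be flagged as hypersensitivity, not as anaphylaxis.

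How often a pair is split depends on when onsets occur. Midnight falls 24 − h hours after the start, so 16 hours after an 08:00 start and 8 hours after a 16:00 start.

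- Both onsets in the first 6 hours: 6 is below 8, so 0% are split for any start in the range.
- First onset uniform over 0 to 22 hours, second following by a uniform 0 to 2 hours: mean gap / 22 = 1/22 = 4.5%.
- Both onsets independent and uniform over 24 hours: 2(h/24)(1 − h/24), which gives 44% at 08:00 or 16:00, 49% at 10:00 and 50% at 12:00. This is an upper illustration; nothing in the SAPs supports an even spread.

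**2. The 00:00 assumption.** Take a 10:00 infusion and an event with true onset at 10:40, a recorded stop time that day and no start time.

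- True relative time: 10:40 − 10:00 = +40 minutes, inside the window.
- With the assumed start: 00:00 − 10:00 = −600 minutes, outside the window. Across the assumed range the value runs from −480 minutes (08:00) to −960 minutes (16:00), always before the infusion.
- On Cycle 1 Day 1 the period rule in 8.2 would return Screening. The TEAE rule looks only at the date and keeps the event as treatment-emergent. The listing would then show a TEAE with onset in Screening.

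This also runs against the SAPs' own handling of missing onset dates, which resolves doubt towards treatment-emergent.

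**3. Next-day events.** Clock times are optional on the day after an infusion, yet part of the window falls there. No rule says whether an untimed next-day event is inside it.

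**The case against.** The strongest reply is that these are edge cases with several safeguards, and much of it stands.

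- A reader might infer that every untimed infusion-day event is set to 00:00. It is not: the rule needs a stop time and a missing start time. An event with dates only gets a duration in days and no clock time. Times are to be collected on infusion days, so this is a fallback for a data gap.
- No text says that the assumed time feeds the reaction flag. The AE listing in 8.2 points the other way: it shows time since infusion when an onset time is recorded and days otherwise. Exclusion from the window is a possible programming result, not a stated one.
- A reader might infer that reactions disappear. They stay in the TEAE tables and listings. Some split pairs also reach review: dyspnoea before midnight with hypotension after it would, because hypotension is a listed symptom.
- A reader might infer that every error undercounts. A stop-time-only event the day after a 10:00 infusion, with true onset at 15:00 (14 + 15 = 29 hours), would move to 14 hours and enter the window. Same-date pairing also joins a cough at 00:30 to a rash at 23:30, 23 hours later.
- The share of the window after midnight (10/24 = 42% for a 10:00 start, 14/24 = 58% for 14:00) measures clock time, not reactions, and cannot be read as a loss.
- The closing paragraph of 8.2.2, under which other AEs "which result in a temporary interruption or permanent discontinuation of a UCB6114 infusion will not be considered as an infusion-related reaction", is a definitional choice. It applies only to events not identified by the preceding rules, and such events have their own tables. It is not an error.

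DLTs are judged by the investigator and the Safety Monitoring Committee reviews sentinel safety data directly, so neither depends on these flags. What the reply does not answer is that 13.1 states a date rule that conflicts with 8.2.2, and that the 00:00 assumption has no stated limit.

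**Conclusion.** The point holds as a mismatch between rules in both SAPs. The pairing defect follows from the text. The 00:00 defect follows from a literal reading that the SAPs leave open, and its clearest result is the conflict between a Screening period and TEAE status on Cycle 1 Day 1. The handling of untimed next-day events is a related gap.

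The size cannot be fixed from the documents, because infusion start times and the distribution of onsets are not given. It is probably small: if reactions cluster soon after a daytime infusion, or the two onsets are close together, few or no pairs are split. The effect is confined to the infusion-reaction and anaphylaxis flags and the period of onset in the listing. The primary TEAE and DLT summaries do not change. The correction is still worth making because it is cheap and replaces stated rules that can misclassify events.

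**What to change.** In both SAPs:

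1. In Part A 4.2.3 and Part A1 4.4.1, state that the 00:00/23:59 assumption is used for AE duration only. For infusion-reaction flagging and period of onset, treat an infusion-day event with no start time as not before the start of that infusion, unless its stop time is earlier.
2. In 13.1, keep same-date pairs and add, as candidates, B+C, D+B or D+C pairs in which both onsets fall within 24 hours after the start of the same infusion. The existing medical review confirms or rejects them. That review matters here, because a 24-hour pairing rule without it would be loose.
3. In 8.2.2, send an untimed event dated the day after an infusion to the same review as potentially within the window.

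The closing paragraph of 8.2.2 needs no change. The cost is SAP wording, small programming changes and a few more candidate events, some of which the review will reject.

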4.4.2 Impact of COVID-19

The FDA and European Medicines Agency (EMA) have provided guidance (see references listed in [Section 12](#)) to help assure the safety of all trial participants, maintaining compliance with good clinical practice (GCP), and minimizing risks to trial integrity during the COVID-19 pandemic. At the time of writing this SAP, the impact of the pandemic is still evolving, and regulators continue to clarify their position, and how to handle missing or delayed assessments resulting from the pandemic is part of the risk assessment of the impact of COVID-19 on trial integrity. For this purpose, the impact at a visit level will be assessed by data collected on a specific COVID-19 impact eCRF form and protocol deviations related to COVID-19. Due to the timing of the start-up of recruitment of participants into this study, the consequences for Part A1 are not expected to be significant and, as a result, no details on strategies for handling missing data are included in this version of the SAP. However, should the ongoing review of COVID-19-related protocol deviations suggest that the impact is more significant than expected, e.g. in the case of a new wave, the SAP may be updated to include further details of handling missing data and/or any sensitivity analyses required. Note that there are no guidelines regarding how much missing data is too much, and there is no proportion of missing data under which valid results and preservation of study power can be guaranteed.

